Attg Surgeon or Surgical house staff research team members	Assess candidacy of patients for enrollment in study *Patients to be randomized into either EGD vs ViSiGi calibration sleeve gastrectomy *Pre-op education on ViSiGI usage via rep and online videos, instruction sheet for surgeons involved	EGD vs ViSiGi device usage for sleeve *No SPECIMEN COLLECTED *Standardize surgeon technique *Fill out Powernote template collecting all intraop data	Assess for complicati on & document in Exemplo	*medical bariatricia n f/u at 2mo *obtain cost data	Assess long- term weight loss, Compile tables, figures etc for abstract and manuscript generation
Study coordinator	Enroll, research consent process, administer	Ensure powernotes are		GERD- HRQL (in	GERD-HRQL (in person or phone)

	baseline GERD- HRQL, notify data analyst *Save hard copy of consent, paperwork in MOT7	done collection intraop data *notify data analyst		person or phone)	
Data Analyst	Enter patient as enrolled in Exemplo data base along with PHI, demographics, etc.	Enter OR date in Exemplo database along with operative duration and stapler information (HER op note, PowerNote with template for all pertinent data)	Assess for complicati on in EHR	EHR review for any 30- day post- op issues, GERD data entry, enter cost data as able	Query MBSAQIP for any post-op issues & weight loss data, enter GERD data entry, Assist w/ tables, figures etc for abstract and manuscript generation
Statistician	NA				TBD

5. Procedures Involved

- Pre-operative period & Bariatrical Surgical consult (usually 1-2 mo prior to surgery) period:
 - Assessing candidacy for study enrollment, research consent process, surgeon education on device, and GERD-HRQL for diagnostic and research purposes
 - Patients will be randomized to either the EGD vs. the ViSiGi device for sleeve gastrectomy calibration
 - o Neither the surgeon nor patient will be blinded to the device used
 - Patients will find out if they are in the EGD vs. ViSiGi device group preoperatively
- Day of surgery = Postop Day zero (POD0)
 - Use of EGD vs. ViSiGi calibration for sleeve intended for therapeutic and research purposes for surgeon

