- Risks/discomforts of EGD and ViSiGi device are comparable. Using a ViSiGi device is similar to both a standard weighted bougie and an EGD calibration technique. The ViSiGi device is similar to a gastroscope in that they both have suction, calibration, and leak testing capabilities. The benefit of the ViSiGi device is that it obviates the need for doing an EGD during sleeve gastrectomy, is single patient use and thus does not require reprocessing, and doesn't require a scope tower to operate it. Potential benefits of using the ViSiGi device (in lieu of endoscopic calibration) in order of highest probability are as follows: 1) less staple loads, 2) shorter OR time, 3) reduced cost, 4) decreased post-op GERD rates.
- Data analyst and study coordinator to have research roles at this time
- Immediate post-op follow-up 3 weeks after surgery (+/- 2 weeks) to 12 months out (+/- 12 months)
 - Assessments made by surgeon will be for diagnostic, therapeutic and research purposes as appropriate
 - Study coordinator and data analyst will function in research roles only
 - Goal in this period is predominantly research purposes only
 - Due to constraints from COVID-19 and decreased in-person follow-up, the 12-month assessment time frame will be extended to 24 months post-surgery to help gather GERD-HRQL and weight loss data
 - a. What type of information will be collected:
 - i. See above table
 - ii. Demographic and clinical variables will be collected at (baseline) including age, gender, race, BMI, smoking status, functional status, and medical comorbidities:
 - 1. EHR
 - 2. MBSAQIP
 - 3. Baseline GERD-HRQL scores (standardized questionnaire)
 - iii. Intra-operative/procedure data (i.e. type of stapler used, # staple load firings, length and color stapler loads, etc.)
 - 1. EHR
 - 2. Research data sheets
 - iv. Post-operative data & assessment
 - 1. EHR
 - 2. MBSAQIP (30-day outcomes and weight loss outcomes)
 - 3. Cost data (administrative data) from internal databases
 - 4. GERD-HRQL scores (standardized questionnaire)

6. Inclusion and Exclusion Criteria

Patients selected for this study will be adults, 18 years old or older, who have already agreed with their surgeon that LSG is the best choice for them. Patients will be excluded by the following criteria;

- Subjects with prior gastric surgery or bariatric surgery (including prior adjustable gastric band and/or sleeve gastrectomy).
- Concomitant hiatal surgery
- Paraesophageal hernia at time of surgery

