There will be 50 patients undergoing LSG with an endoscope and 50 patients undergoing LSG with a suction calibration system. Both methods are clinically accepted and approved methods of performing the procedure. The target enrollment will be 125 to account for attrition due to screen failures, early withdrawals, etc. For this study we use a randomized block design (RBD) to assign participants to one of two sleeve groups. In a RBD we divide participants into subgroups called blocks (e.g. gender, race, etc.), such that the variability within blocks is less than the variability between blocks. Then, subjects within each block are randomly assigned to treatment conditions (i.e. SG with EGD or SG with ViSiGi device). The purpose of the RBD is to help reduce variability within treatment conditions and potential confounding from blocking factors, producing a better estimate of treatment effects. We are adequately powered to detect a mean difference in stapler load firings of 0.4 between groups assuming a standard deviation of 0.7, which is consistent with our institutional sleeve gastrectomy experience. After all cases have been performed statistical methods will be implemented to determine any difference in outcomes. An initial approach will focus on a pairwise analysis (t-test) between the ViSiGi and EGD calibration groups for each of the primary and secondary aims. A more comprehensive multivariate analysis factoring in demographic and clinical variables will be performed to further delineate significant differences in the 2 sleeve gastrectomy methods. In the unlikely situation that an adverse event occurs, the event will be inspected to determine if an early stoppage is necessary.

14. Provisions to Monitor the Data to Ensure the Safety of Participants

All methods used in this study for performing sleeve gastrectomy are already approved and clinically accepted. Validated users of the device will be attending surgeons who have been trained using the ViSiGi device via online video-based education

(https://www.youtube.com/watch?v=zDhc-1fr32E), review of the manufacturer instructions for use (IFU) sheet below:

(chromeextension://oemmndcbldboiebfnladdacbdfmadadm/https://www.boehringerlabs.com/wp-content/uploads/2018/09/5232009.pdf) as well as in-person education via representatives from Boehringer Laboratories, LLC.

All surgeons will be required to complete the video-based module and review the IFU sheet prior to using the ViSiGi device.

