detailed analysis of safety issues including the incidence of AEs, clinical severity of AEs, serious AEs, UPs, deaths and protocol deviations. The PI will also document receipt and review of these safety reports in addition to any corrective actions and/or resolutions to findings reported which will also be reported to the IRB.

The sponsor does not have any additional reporting requirement than what Emory Hospital already has in place.

15. Economic Burden to Participants

N/A

16. Informed Consent Process

Consent will be obtained in person before the patient undergoes surgery by the principal investigator, co-investigators, and/or research study coordinator. Consent will likely occur at the initial surgical consultation, but may be obtained at any point prior to randomization. Patients will be notified if they are going to be in the EGD vs. ViSiGi device arm of the sleeve gastrectomy protocol during the perioperative period; it will be explained to them that this selection is being done in a randomized fashion, similar to flipping a coin, factoring in various patient-related factors. No elements of HIPAA will be waived. The study participants are legal adults and not pregnant, prisoners, or otherwise cognitively impaired in any way.

DocuSign:

The study team will use an Emory DocuSign account that is HIPAA compliant and meets the FDA's requirement for CFR Part 11 signatures. The consent process begins when a patient is screened and identified as eligible for study participation. A member from the study team will discuss the informed consent form in its entirety with the potential participant via telephone phone and/or Zoom. The patient's identity will be verified by requesting that he/she confirm their demographical information (i.e. full name, DOB, address, etc.).

In DocuSign, potential subjects have the ability to review the consent document as freely as they would if they were consenting in person. They also have the opportunity to exit the document without signing. The patient will be offered ample time to discuss the informed consent form with family and or friends, and have questions answered.

The process for obtaining final consent is outlined below:

1. First, the IRB-approved, stamped informed consent form(s) are added to an envelope in DocuSign.

- Secondly, recipients (subjects/coordinators) are then added to the envelope and signature and initial fields are assigned to them on the IRB approved informed consent form.

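### Randomisation is placed weeks before the operation that produces the primary endpoint, so cancellations, withdrawals and exclusions at surgery become losses after allocation in an unblinded trial

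*Combined protocol and SAP*

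**What the plan says.** **Timing of allocation.** The Section 4 table puts randomisation in the pre-operative and consult column, not the day-of-surgery column. Section 5 does the same: "Patients will be randomized to either the EGD vs. the ViSiGi device for sleeve gastrectomy calibration" appears under the heading "Pre-operative period & Bariatrical Surgical consult (usually 1-2 mo prior to surgery) period". Section 16 adds "Consent will likely occur at the initial surgical consultation, but may be obtained at any point prior to randomization".

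**Knowledge of the arm.** Section 5 states "Neither the surgeon nor patient will be blinded to the device used" and "Patients will find out if they are in the EGD vs. ViSiGi device group preoperatively". Section 16 is looser, referring only to the time around the operation: "Patients will be notified if they are going to be in the EGD vs. ViSiGi device arm of the sleeve gastrectomy protocol during the perioperative".

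**Exclusions.** Section 6 lists "Paraesophageal hernia at time of surgery" and hiatal surgery done at the same operation. It also excludes a woman who becomes pregnant at any point in the study.

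**Numbers.** Sections 7 and 13 plan for 50 patients operated on in each arm. Section 13 adds: "The target enrollment will be 125 to account for attrition due to screen failures, early withdrawals, etc". It does not divide that allowance into loss before and after randomisation. No analysis population is defined, and nothing says how a patient who is randomised but not operated on, or is excluded at surgery, is handled or replaced.

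**Baseline GERD score.** The synopsis places the baseline questionnaire on the operative day. The Section 4 table and Section 5 place it in the pre-operative period.

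**The concern.** The firing count arises at one event, the operation. If allocation comes weeks earlier, everything that stops a patient reaching that event, or removes the patient at it, happens after randomisation. Three routes are open: cancellation or a change of procedure, withdrawal, and an exclusion first established in theatre.

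For a patient who never has the sleeve, no analysis rule can supply the missing count. For a patient who meets an exclusion at surgery but still has the sleeve, the count exists, but the plan does not say whether it is used, and the surgeon who applies the exclusion knows the arm.

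Section 5 itself lists the benefits hoped for from the suction device, so patients and surgeons may have a preference and time to act on it. If loss depends on the arm, the comparison is no longer between randomised groups but between those who remained. An operative-day baseline GERD questionnaire could also be answered with the arm already known.

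**Working it through.** **1. The plan's own numbers (Section 13).** Inputs: difference 0.4 firings, SD 0.7, 50 per arm. Alpha, sidedness and power are not stated; I assume two-sided 0.05 and 80%.
- Required n per arm = 2 × (1.960 + 0.842)² × 0.7² / 0.4² = 48.1, so 49. The stated 50 is reproduced. The exact t-test needs 50.
- Power at 50 per arm: 0.4 / (0.7 × √(2/50)) = 2.857, and 2.857 − 1.960 = 0.897, giving 81.5% (80.8% by the exact t-test).
- Enrolment: 100 / (1 − 0.20) = 125, so the allowance is 25/125 = 20%.

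**2. Loss of numbers.** Suppose all 125 are randomised and a share has no firing count (same assumptions, normal approximation):
- 10% lost: 112.5 evaluable, power 85.8%
- 20% lost: 100 evaluable, power 81.5%
- 25% lost: 93.75 evaluable, power 79.0%
- 30% lost: 87.5 evaluable, power 76.2%

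Power stays above 80% up to the planned 20% loss and falls just below it at 25%.

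**3. Loss of comparability.** Let an arm lose a share d of its randomised patients, and let the lost patients differ from the retained by g firings on average, had they been operated on. The full-arm mean is the retained mean + d × g, so the retained mean is off by d × g. With the same g in both arms, the bias in the difference is (d₁ − d₂) × g. The documents give neither the d values nor g, so all inputs here are assumptions:
- Mild case: 15% v 20%, g = 0.2. Shifts 0.03 and 0.04; bias 0.01 firings, or 0.01/0.4 = 2.5% of the target difference.
- Severe case: 10% v 30%, g = 0.5. Shifts 0.05 and 0.15; bias 0.10 firings, or 0.10/0.4 = 25% of the target.
- Equal loss of similar patients in both arms: bias zero.

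The severe case averages 20% loss, so it treats the whole allowance as falling after randomisation, although the allowance includes screen failures. Its gap of 0.5 is 0.5/0.7 = 0.71 SD. It is an upper illustration, not an estimate.

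**4. Timing against eligibility.** Section 5 assesses candidacy in the pre-operative period. Section 6 ties the paraesophageal hernia exclusion to the time of surgery, and concomitant hiatal surgery can be known for certain only once the operation is under way. Eligibility can therefore remain open after allocation.

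**The case against.** Randomising before the day of surgery is a legitimate choice in an open-label device trial, where the scope or the suction device has to be arranged. Participants have already agreed to the sleeve with their surgeon, and Sections 5 and 9 describe the two techniques as having comparable or similar risk. The documents give no evidence that patients leave because of their arm, or that those who leave would need a different number of firings. Enrolment is already raised for attrition. All of this stands, and it limits the point to a risk of bias of unknown size.

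Three stronger readings are tempting, and the documents do not support them:
- A reader might infer that eligibility is settled at the consult. It is not: two exclusions are tied to the operation, and pregnancy can arise at any time. This opens a further route of loss, with an unblinded decision at the end of it.
- A reader might infer that every patient is randomised at the consult visit, 1-2 months ahead. The text gives a period, qualified by usually, and Section 16 allows consent at any point before randomisation. The exact moment is unspecified.
- A reader might infer that the trial is underpowered by this loss. Up to the planned 20%, it is not.

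The objection does not answer the central difficulty. Extra enrolment replaces numbers, not the patients lost from a particular arm, and the plan has no rule for handling those losses.

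**Conclusion.** The concern holds as a weakness of design that should be corrected. Allocation is placed in a period usually 1-2 months before the only event that yields the primary endpoint, without blinding, and with some exclusions possibly established only at that event. The issue is comparability of the arms, not sample size: 50 per arm gives about 81% power under an assumed two-sided 0.05, and 125 covers a 20% loss.

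The bias cannot be estimated from the documents. The illustrations run from 0.01 to 0.10 firings against a target of 0.4, rest wholly on assumed loss rates and gaps, and assume the same gap in both arms. The figure of 0.10 should not be read as a finding about this trial. With equal, unselective loss the only cost is numbers.

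A reader might also infer that allocating on the day of surgery would remove the problem entirely. It would not: a pre-operative re-check cannot catch a hernia first found in theatre, so an analysis rule and reporting by arm are needed as well.

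**What to change.** - **Section 4 table and Section 5:** keep consent before randomisation. Move randomisation and release of the arm to the day of surgery, after the Section 6 criteria have been re-checked and once the sleeve is going ahead. Where feasible, allocate after the operative check for the two hiatal exclusions.
- **Baseline GERD-HRQL:** require completion before the arm is released, and reconcile the synopsis (operative day) with Sections 4 and 5 (pre-operative).
- **Section 13:** analyse all randomised patients who have a sleeve gastrectomy in the arm to which they were allocated. State how patients found to meet an exclusion after allocation are handled.
- **Reporting:** give the numbers consented, randomised, operated on and excluded, with reasons, by arm from randomisation onward.
- **Sections 5 and 16:** agree on when the patient is told the arm.

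The cost is mainly protocol wording. The allocation must be obtainable on the day with both devices available. Patients learn their arm only on the day, or after surgery if allocation is made during the operation; in the latter case the Section 5 statement that they are told preoperatively would have to change.

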- Any subject with prescribed immunosuppressive drugs.
- In the opinion of investigator, subject is not eligible to participate in the study.
- If patient is a female and becomes pregnant at any time during the study duration

7. Local Number of Participants

There is no additional screening for the study that the patient would already be subject to if they were not part of the study. There will be 50 patients undergoing LSG with an endoscope and 50 patients undergoing LSG with a suction calibration system. Patients will be assigned randomly to each group.

8. Recruitment Methods

9. Subjects will be identified by the 1) treating physician/surgeon and/or her clinical staff or 2) the study staff reviewing clinic and/or hospital admissions. Risk to Participants

The risk for participating in this study is expected to be minimal and equivalent to standard peri-operative morbidity and mortality associated with sleeve gastrectomy. Moreover, patient safety and risk profiles are expected to be similar between the endoscopic vs. suction device calibration techniques. A rare complication associated with laparoscopic bariatric is tube/probe stapling during sleeve gastrectomy. Given that the ViSiGi device is a plastic tube it could potentially be stapled across during gastrectomy or cause other trauma to the stomach or esophagus with intra-operative manipulation during sleeve gastrectomy. It is also possible for a gastroscope to be stapled across during gastrectomy and to cause mucosal trauma with manipulation and suctioning during sleeve gastrectomy. Again, the overall risk directly associated with intra-operative use of either the ViSiGi or endoscopic devices during sleeve gastrectomy risk anticipated to be minimal (< 1%) and similar between groups.

10. Potential Benefits to Participants

This study, by its nature, will be focusing on bariatric surgery and therefore people with obesity who meet standard NIH criteria for weight loss procedures like LSG (5). The information from this study may help the community by giving the hospital information on ways to more effectively and efficiently perform LSG.

11. Compensation to Participants

There will be no patient reimbursement for participation in this study.

12. Data Management and Confidentiality

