Data for this study will be recorded on a secure password-protected electronic database called **Exemplo**. Data entry will be done by study investigators and/or data analysts who are part of the approved IRB team. Unidentified data may be shared with the sponsor, Boehringer Laboratories LLC.

Data analysis will be done by internal or externally hired statisticians on de-identified data on spreadsheets downloaded from **Exemplo**.

Separate intra-operative data will be collected from the EHR either via the Operative Note or via standardized PowerNote templates (**if available**) to help capture data pertinent during sleeve gastrectomy including the following:

- 1) Patient Full Name: pre-populated/pull from eEMR
- MRN: pre-populated/pull from eEMR
- 3) **Date of surgery**: pre-populated/pull from eEMR
- 4) **Primary Surgeon**: pre-populated/pull from eEMR
- 5) **Stapler used**: Echelon Flex Powered 60mm stapler, Endo GIA 60 mm Universal Stapler XL; Other (free text)
- 6) **Distance from pylorus for 1**st **stapler firing**: Free text for centimeters
- 7) **Calibration device**: EGD/Standard Weighted Bougie Tapered/Standard Weighted Bougie Blunt/ViSiGi device/Other (free text)
- 8) Calibration device size: free text for French
- 9) Total number of stapler load firings: free text number
- 10) **Length of stapler loads used** (list number): 60 mm(free text number or click n/a); 45 mm (free text number or click n/a); other (free text)
- 11) **Number, order & color of stapler loads** (first to last; i.e. 2 green, 2 gold, 1 blue): free text
- 12) Use of Seam Guard reinforcement for stapler loads: yes/no
 - a. If yes, were all stapler loads reinforced? Yes/no; other (free text)
- 13) Other procedures performed:

- a. Plication/imbricating suture to sleeve: yes/no; other (free text)
- b. Pexy of omentum to sleeve: yes/no; other (free text)
- c. Clipping of sleeve staple line: yes/no; other (free text)
- d. Oversewing staple line: yes/no; other (free text)
- e. Fibrin glue to staple line: yes/no; other (free text)
- f. Any other procedures?: free text

14) **EGD done**: yes/no

- a. If yes, any abnormal findings: yes/no; other (free text)
- b. If abnormal findings, please list any interventions done: free text
- 15) Miscellaneous Notes: free text

13. Statistical Analysis

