The PI will be responsible for ensuring participants' safety on a weekly basis as cases are performed (sleeve gastrectomies are not always done every week) and for reporting serious Adverse Events (AEs) and Unanticipated Problems (UPs) to his or her Institutional Review Board (IRB) and the monitoring body with the help of the study coordinator. The study coordinator and/or PI will prepare reports that list AEs, serious AEs, deaths, and disease-or treatment-specific events required for MB review in order to ensure good clinical care and identify any concerning trends. The Monitoring Body (MB) will act in an advisory capacity to the PI to monitor participant safety, evaluate adverse events and progress of the study. The MB will constitute two surgeons who are not directly involved in the study protocol but participate in the care of bariatric patients at Emory University Hospital Midtown and will to review the safety data annually.

The PI will be informed of serious AEs as soon as they occur by Co-Investigators (i.e., surgeons performing sleeve gastrectomy) and/or the study coordinator and notify the MB within 48 hours of becoming aware of the event. The PI will report serious AEs and UPs to his or her IRB within 5 business days of becoming aware of the event. Events constituting UPs include calibration device malfunctions such as a piece or component of the device breaking off into the stomach during manipulation, failure of the device to adequately perform a leak test, or contamination or damage to the device such that it cannot be appropriately used. Specific triggers for an ad hoc review or initiation of the process of an ad hoc review will occur if there are unforeseen deaths or if there is a serious AE including stapling across a calibration device during sleeve gastrectomy or other serious device malfunction leading to patient injury. At any point during the study time period, the study will be stopped and undergo further review if ≥ 1 deaths or a serious AE directly related to calibration device use (i.e., stapling across device while creating sleeve gastrectomy or serious device malfunction leading to patient injury) occurs.

Safety reports will be sent to the MB for review after the first 5 subjects are enrolled and within 12 months of the study start date. Safety assessment reports will provide a

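### The intra-operative template has no structured item, in either arm, for the device events the plan names, and its only abnormal-findings prompt depends on an EGD being done

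*Combined protocol and SAP*

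**What the plan says.** The surgeon's row of the Section 4 table gives the template a wide scope on the day of surgery: "Fill out Powernote template collecting all intraop data". Section 12 then lists 15 items, introduced as "to help capture data pertinent during sleeve gastrectomy including the following". Item 14 asks whether an EGD was done. If it was, 14a asks "If yes, any abnormal findings: yes/no; other (free text" and 14b adds "If abnormal findings, please list any interventions done: free text". Item 15 is "Miscellaneous Notes: free text".

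Section 9 names harms of both devices. Of the suction device it says "Given that the ViSiGi device is a plastic tube it could potentially be stapled across during gastrectomy" and that it may injure the stomach or esophagus. It says that a gastroscope can also be stapled across and can injure the mucosa. It expects the device-related risk to be below 1% and alike in the two groups.

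Section 14 counts device malfunctions as UPs, including a part breaking off in the stomach and "failure of the device to adequately perform a leak test, or contamination or damage to the device such that it cannot be appropriately used". Stapling across a calibration device is a trigger for ad hoc review and for stopping. The safety reports are to give the incidence of adverse events and UPs.

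Section 5 says of the ViSiGi device that "it obviates the need for doing an EGD during sleeve gastrectomy".

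**The concern.** The plan names specific device events and undertakes to report how often they occur, but the form filled in at surgery does not ask about them. Whether a leak test failed without injury, or a device was damaged and exchanged, is known in the operating room. If nobody is asked then, it cannot be reliably recovered from later chart review.

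The one prompt for something abnormal opens only after an EGD. Because the suction device is meant to replace the EGD, that prompt will in practice follow the randomised arm. Mucosal injury seen at endoscopy would be asked about in most EGD patients and in few ViSiGi patients. Surgeons are not blinded, so what is volunteered in free text may also depend on the device.

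At stake are the completeness of the adverse-event and UP counts in the safety reports, and whether the expectation of similar risk in the two groups can be examined at all.

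**Working it through.** **Step 1. Named events against the template (Section 12, items 1 to 15).**

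| Event | Where the plan names it | Prompt in EGD arm | Prompt in ViSiGi arm |
|---|---|---|---|
| Device stapled across | Section 9, risk; Section 14, review and stop trigger | none | none |
| Part of device breaks off | Section 14, UP | none | none |
| Contamination or damage | Section 14, UP | none | none |
| Leak test not adequately performed | Section 14, UP | none | none |
| Mucosal, gastric or esophageal trauma | Section 9, risk | indirect, through 14a-b if seen at endoscopy | none, unless an EGD is done |

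The first four rows are the same in both arms: capture is incomplete, not unequal. Only the last row differs, and it differs by whether an EGD was done. That follows the arm only because Section 5 presents the suction device as making the EGD unnecessary.

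**Step 2. Other places on the form.** Item 7 records the calibration device, with a free-text alternative, but asks neither about an exchange nor its reason. Item 13f asks about other procedures, so a repair could be entered in either arm. Item 15 is open to both arms but prompts for nothing.

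**Step 3. Routes outside the form.** Under Section 14, co-investigators or the coordinator tell the PI of serious adverse events as they occur, and the PI notifies the Monitoring Body within 48 hours. The PI reports serious adverse events and UPs to the IRB within 5 business days of becoming aware of them. The UP and stop wording refers to the calibration device generally, so it covers both arms. For a UP that is not serious, no step says how the PI becomes aware. The later checks (3 weeks, 30-day chart review, MBSAQIP) are post-operative, and the plan names no device event for them.

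**Step 4. Scale.** The only figure the plan gives on this point is the expected risk below 1%, stated without derivation. With n = 50 per arm (Sections 7 and 13), true risk p and independent patients:

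- Expected events per arm = n × p. At p = 1%: 50 × 0.01 = 0.5. At p = 0.5%: 50 × 0.005 = 0.25.
- Chance of at least one event in an arm = 1 − (1 − p)^50. At 1%: 1 − 0.99^50 = 39%. At 0.5%: 22%.
- Chance of at least one in the trial = 1 − (1 − p)^100. At 1%: 1 − 0.99^100 = 63%. At 0.5%: 39%.

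The 1% is the plan's upper bound; the 0.5% is an assumed lower value. With counts this small, one unrecorded event could change how the arms compare. Recorded events would be n × p × c, where c is the capture rate in that arm. The documents give no c for either arm, so the imbalance cannot be calculated.

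**Step 5. What is untouched.** The sample size rests on a difference of 0.4 firings with SD 0.7, and item 9 records the number of firings in both arms. Neither depends on the missing items.

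**The case against.** The strongest reply is that the form is not the safety system. Item 14 records endoscopic findings, is not labelled an adverse-event field, and opens for any patient in either arm who has an EGD. The item list is introduced as inclusive rather than complete. Section 12 also allows the Operative Note as a source, and Section 5 mentions research data sheets whose content is not shown. Section 14 makes the PI responsible for safety week by week and has its own reporting chain. No between-arm safety test is planned: the aims are firings, time, cost, GERD and weight loss. Nor would better recording make the arms comparable with any precision: zero events in 50 patients leaves a one-sided 95% upper bound of 1 − 0.05^(1/50) = 5.8%, against an expected risk below 1%.

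Most of this stands, and it limits the point. A reader might infer that harm is recorded unequally in favour of the suction device, or that the stop rule is compromised. The documents support neither. The device-event gap is common to both arms, and the Section 14 stop rule turns on deaths and serious device-related events, which have a route that does not depend on the form or the arm. A reader might also assume capture rates and derive a ratio between arms, but that ratio would only restate the assumption.

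What the reply does not meet is the non-serious event. An inclusive list leaves room for further items but commits to none, a narrative note prompts for nothing, and weekly oversight does not say what is looked at.

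**Conclusion.** The point holds in a limited form. The template has no structured item in either arm for the device events the plan names, and no route is stated by which a non-serious UP reaches the PI. Non-serious device events may therefore be under-recorded in both arms. Separately, mucosal findings may be prompted mainly in the EGD arm. That is a risk of differential ascertainment, not a demonstrated bias, and its size cannot be computed from the documents.

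The conclusion rests on two assumptions: that EGD use follows the arm closely, as Section 5 implies, and that the research data sheets, which are not shown, carry no equivalent items. The primary endpoint, the sample size and the serious-event stop rule are not shown to be affected. This is a cheap improvement, not a flaw that threatens the trial's main result.

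**What to change.** Add the same yes/no items to the template and to the Exemplo database, completed for every patient whichever device is used:

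- leak test done, and its result;
- calibration-device malfunction, breakage or contamination;
- device stapled;
- visible mucosal or esophageal injury;
- change of calibration device, with the reason.

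Use these common items for the adverse-event and UP incidences in the Section 14 safety reports, shown by arm. Keep item 14 as a record of endoscopic findings and do not use it to compare safety between arms. State in Section 14 how a non-serious UP reaches the PI; a yes on one of these items could serve as that notice.

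The cost is five short items, about a minute per case, and matching database fields. The small downside is that more minor events will be recorded.
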